Comparison of Therapeutic Effects of Greater Occipital Nerve Blockade, Topiramate and Flunarazine in Episodic Migraine

07.07.2019

Objective: The preventive drug therapy in migraine is for reducing the attack frequency, severity and duration of the headache. Flunarizine and topiramate are widely used in the prevention of migraine attacks. Greater occipital nerve block (GONB) is an alternative treatment option which is used in the prophylactic treatment of migraine. In this study we compared the effectiveness of GONB, topiramate and flunarizine by means of reduction in post treatment VAS scores and attack frequencies in episodic migraine patients in a one month period.

Material and Methods: One hundred and twenty migraine patients were aimed to be divided into three treatment groups namely flunarazine, topiramate and GONB. Patients were followed for 4 weeks and attack frequencies and VAS scores were recorded weekly. At the end of fourth week, response rates, rates of 50% and 75% or more reduction in VAS and attack frequencies were calculated. Groups wise comparisons were assessed statistically.

Treatment protocol

Flunarizine was introduced with a single dose of 10 mg/day. Topiramate was administered twice a day at a dose of 25 mg/day, which was increased to 100 mg/day in the second week. The GONB solution was prepared with 1 ml triamcinolone (40mg), 2 ml bupivacaine (10 mg), and 1 ml 0,9% NaCl. The solution was administered using a 22G × 1¼" (0.7 × 40mm) injector with the patient lying prone on the table. Injection was applied to medial of the occipital artery localized at the medial one-third of the superior nuchal line between the occipital tubercle and

mastoid process. The scalp was cleaned with iodine before the procedure, and the injections were performed bilaterally at a volume of 2 mL after negative aspiration for blood.

Statistical analysis

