Normality of distribution was assessed with the D'Agostino-Pearson test. Continuous variables with a normal distribution were assessed in two or more groups using the Student's t-test and ANOVA test, respectively. Non-parametric counterparts of these tests (Mann Whitney U and Kruskal-Wallis tests) were utilized to compare the data that were not normally distributed. Nominal categorical data were assessed using the chi-square test. The pre- and post-treatment comparison of normally and non-normally distributed data were undertaken using the paired t-test and the Wilcoxon test, respectively. A two-tailed p value of <0.05 was considered to be statistically significant.

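### Do the pre/post tests, which share the p<0.05 rule with the between-arm tests, need to be labelled descriptive?

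*Combined protocol and SAP*

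**What the plan says.** The purpose is comparative. The title announces a comparison of the three treatments, the Objective says "In this study we compared the effectiveness of GONB, topiramate and flunarizine", judged by the reduction in VAS and attack frequency over one month, and Material and Methods adds "Groups wise comparisons were assessed statistically". On size and arms: "One hundred and twenty migraine patients were aimed to be divided into three treatment groups namely flunarazine, topiramate and GONB". No placebo or untreated arm is described.

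The Statistical analysis section gives a between-group test for each kind of data. For normal data it says: "Continuous variables with a normal distribution were assessed in two or more groups using the Student's t-test and ANOVA test, respectively". Skewed data go to the rank-based equivalents, and categories to chi-square. The section then adds the pre/post tests: "The pre- and post-treatment comparison of normally and non-normally distributed data were undertaken using the paired t-test and the Wilcoxon test, respectively". It does not say whether these are run arm by arm or on all patients together. The section closes with a single threshold: "A two-tailed p value of <0.05 was considered to be statistically significant". It does not state which family of tests supports a conclusion about effectiveness, and it does not call the pre/post results descriptive.

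**The concern.** Two kinds of test stand next to each other under one significance rule, with no order between them. In a trial with three active arms this invites two familiar errors. The first is to read a significant fall within an arm as proof that the treatment works, although patients who enter with frequent or severe attacks tend to improve over a month anyway. The second is to read significance in one arm and non-significance in another as a difference between treatments. If either reading reached the conclusions, the report could claim efficacy that the design cannot show, or rank treatments that are in fact equal.

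**Working it through.** **1. The sections side by side.** Title, Objective and Material and Methods state only between-arm purposes; none sets a within-arm aim. The Statistical analysis section matches this with a between-arm test for normal, non-normal and categorical data. The pre/post sentence names a test for a type of data and draws no inference from it. The threshold sentence says when a p-value is called significant, not what may be claimed from it.

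**2. The two families ask different questions.** Write the mean change in arm k as μk = c + tk, where c is the non-specific change common to all arms and tk the treatment's own effect. The paired test has null μk = 0, so it responds to c. The between-arm test has null μ1 = μ2 = μ3, and c cancels. Three significant falls with a non-significant ANOVA are therefore compatible results. So is a split among the paired tests with a non-significant ANOVA.

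**3. How often the paired tests would mislead if used to rank arms.** The target of 120 cannot be reproduced, because no effect size, SD, power or dropout is given. Inputs:
- From the plan: 120 patients, three arms, two-sided 0.05.
- Assumed: 120/3 = 40 per arm, paired tests run per arm, normal change scores with equal variance, independent arms, one outcome, and the same d = mean change / SD of change in every arm.

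Formulas: p is the two-sided power of the paired t-test, from the noncentral t with 39 degrees of freedom and noncentrality d√40. All three arms significant: p³. Arms split: 1 − p³ − (1 − p)³, which simplifies to 3p(1 − p).

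At d = 0.32: noncentrality 0.32 × 6.325 = 2.02; p = 0.506; all three 0.506³ = 0.13; split 3 × 0.506 × 0.494 = 0.75.

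| d | One arm significant | All three significant | Arms split | Split while ANOVA on change is non-significant (simulated) |
|---|---|---|---|---|
| 0 | 5% | <0.1% | 14% | 10.2% |
| 0.2 | 23% | 1% | 54% | 48.9% |
| 0.32 | 51% | 13% | 75% | 69.8% |
| 0.5 | 87% | 66% | 34% | 29.8% |
| 0.8 | 99.9% | 99.6% | 0.4% | 0.1% |

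The last column comes from 100,000 simulated trials per value of d. In the same trials the ANOVA rejected in 4.9% to 5.2%, its nominal rate, as step 2 predicts. With 30, 40 and 50 per arm, the split at d = 0.32 is 76%.

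**4. What the table does and does not show.** With equal arms, 3p(1 − p) cannot exceed 0.75, reached at p = 0.5; d = 0.32 is simply the value that gives p close to 0.5. Nothing in the plan places d anywhere on the scale. The figures cover the paired t-test only, whereas non-normal data go to Wilcoxon. If the pre/post test pools all patients, there is one test and no split can occur.

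**5. What a label would alter.** It changes neither the sample size, the threshold, the data nor any between-arm test. Replacing the paired t-test by a 95% interval for the mean change would not alter the inference either, since that interval excludes zero exactly when p<0.05.

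**The case for a change.** The best argument for a change is that the comparative priority has to be inferred. The analysis text never makes it a rule, and one sentence would do so at no cost in patients or data. The misreading is a real risk: over the middle of the assumed range, equal treatments would often look different on paired significance while the planned ANOVA finds nothing. At large d the splitting vanishes, but all three falls are then almost always significant, which tempts a reader towards an efficacy claim.

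The facts behind this stand: one threshold, no written hierarchy, no untreated arm. So does the warning about interpretation. What does not follow is that the plan is at fault. A plan need not exclude every misuse of a standard test, and this one states no within-arm aim. Nor would the label decide which between-arm result counts most: change in VAS, change in attack frequency and the response rates would remain on an equal footing, with no primary contrast named. That is a separate question. So is whether the comparison of change is adjusted for baseline, which only asks for a choice to be written down.

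**Conclusion.** No change is called for. This is a gap in wording that an analyst fills sensibly from the stated objective: conclusions about effectiveness rest on the between-arm comparisons, and within-arm changes describe the course in each group. Followed as written, the plan delivers that comparison, and a change shared by all arms does not disturb its error rate (about 5% at every d examined).

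The split rates of 14%, rising to 75% and falling to 0.4%, illustrate a ranking rule that the plan does not contain. They rest on an assumed 40 per arm, per-arm testing, normal changes and a standardised change that the documents do not supply. A sentence calling the within-arm results descriptive would be an optional courtesy to readers. This conclusion concerns only the relation between the two families of tests. It would be different if the text drew efficacy claims or a ranking from the paired p-values, and it does not.

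### No primary endpoint, test order or multiplicity rule for two unranked outcomes and their response rates in three arms, so the chance of a false between-arm finding is about 7–10% or more if any significant result counts

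*Combined protocol and SAP*

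**What the plan says.** The Objective sets out to compare the three treatments "by means of reduction in post treatment VAS scores and attack frequencies". The two outcomes stand side by side and neither is called primary. Material and Methods gives the size and number of arms ("One hundred and twenty migraine patients were aimed to be divided into three treatment groups"), says that "attack frequencies and VAS scores were recorded weekly", and adds for the end of week 4 that "response rates, rates of 50% and 75% or more reduction in VAS and attack frequencies were calculated". On comparing the arms it says only "Groups wise comparisons were assessed statistically".

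The Statistical analysis section chooses tests by data type and number of groups. The sentence beginning "Continuous variables with a normal distribution were assessed in two or more groups using the" assigns the t-test to two groups and ANOVA to more than two, with Mann-Whitney and Kruskal-Wallis as the non-parametric counterparts. For response rates, "Nominal categorical data were assessed using the chi-square test". Within-arm change is tested with the paired t-test or the Wilcoxon test. The section ends with its one decision rule: "A two-tailed p value of <0.05 was considered to be statistically significant".

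Neither part names a primary endpoint, a test order, a gate, a post hoc procedure or an adjustment.

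**The concern.** A 5% level applied to each test limits the error of that test, not the error of the trial's conclusion. The plan produces up to six week-4 endpoints (two outcomes and four response rates) across three arms. It does not say which result is the conclusion, whether one significant outcome is enough or both are needed, whether pairs of arms are tested, or whether the weekly recordings are tested. A reader who sees one p-value below 0.05 among these cannot tell whether the trial succeeded or how often such a result would arise by chance.

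The within-arm tests add a second risk. A pre/post result that is significant in one arm and not in another could be presented as a difference between treatments, which it is not.

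**Working it through.** **Inputs from the plan.** Two-sided 0.05 for each test; two outcomes; two response thresholds on each; three arms; 120 patients in total; weekly recording for 4 weeks. The plan states no family-wise error rate, power, effect size or SD, so there is no overall figure of its own to reproduce. As a check on the method, one simulated three-group ANOVA with equal arms rejects in 5.0% of trials, as it should.

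**Assumptions not in the plan.** Equal split, 120 / 3 = 40 per arm; all arms truly equal; normal outcomes with correlation 0 to 0.9; response rates (50% / 75% threshold) of 50/30, 60/30, 40/15, 70/40 or 30/10 per cent.

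**Two three-group tests, either one sufficient.** With independent outcomes the chance of at least one false positive is 1 − (1 − 0.05)² = 9.75%. Simulation with 200,000 trials per correlation gives:

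| Correlation | ANOVA | Kruskal-Wallis |
|---|---|---|
| 0 | 9.7% | 9.6% |
| 0.5 | 9.2% | 9.1% |
| 0.7 | 8.4% | 8.3% |
| 0.9 | 7.3% | 7.2% |

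The choice of test hardly matters. Even at correlation 0.9 the rate stays above 5%.

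**Other readings that the text leaves open** (20,000 trials per setting):

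| Reading | Correlation 0–0.7 | Correlation 0.9 |
|---|---|---|
| Both outcomes must be significant | 0.2–1.6% | 3% |
| Three-group tests, two outcomes, either sufficient | 8–10% | 7% |
| Three-group tests, all six week-4 endpoints | 18–22% | 17% |
| All pairs without a gate, two outcomes | 19–23% | 16–17% |
| All pairs without a gate, six endpoints, continuity-corrected chi-square | 28–34% | 25–27% |
| The same, uncorrected chi-square | 39–47% | 34–39% |

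The six endpoints overlap heavily, so the independence formula, 1 − 0.95⁶ = 26.5%, overstates the three-group figure. Testing two outcomes at each of the 4 weeks with three-group tests would give 19–29% (correlation between weeks 0.5–0.8, between outcomes 0–0.7). The plan states neither ungated pairs nor weekly tests. These are readings that were simulated, not bounds.

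**Within-arm tests.** Suppose all three arms share the same true change. If p is the power of one paired t-test with n = 40, the chance that the test is significant in some arms but not all is 1 − p³ − (1 − p)³.

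- Change of 0.3 SD: p = 0.457, giving 1 − 0.095 − 0.160, or about 74%.
- Change of 0.5 SD: p = 0.869, giving 1 − 0.657 − 0.002, or about 34%.
- Change of 0.8 SD: p = 0.999, giving under 1%.

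**The case against.** The strongest reply is that the plan never says one significant result is enough. Its 0.05 can be read as a reporting threshold for each test, and the Objective joins the two outcomes with the word and. If both must be significant, the error is below 5%. That is correct, and it is why the inflation is stated as conditional. It does not rescue the plan: the text allows readings that run from under 1% to over 20% and chooses none. Nor does it call the study exploratory; it sets out to compare effectiveness and declares statistical significance.

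A second reply is that the largest percentages belong to analyses the plan does not specify. The t-test is assigned to two groups and ANOVA to more, so the three-arm comparison points to the three-group test, and the weekly values are said only to be recorded. This stands. The conclusion therefore rests on the 7–10% and 17–22% figures, not on ungated pairs or weekly tests.

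Third, the documents do not say that within-arm results will be used to compare treatments, and direct comparison is planned. That is also true. The 74% and 34% are not false-positive rates of the between-arm tests; they show why the within-arm tests need a label.

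Finally, the text is written in the past tense. If the data had been seen, naming a primary now cannot restore error control. This too stands, and the fix allows for it.

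**Conclusion.** The concern holds and must be fixed. The absence of a primary endpoint, test order and multiplicity rule is plain in the text. If any significant between-arm result counts as a finding, the false-positive chance is about 7–10% for three-group tests on the two outcomes and about 17–22% for all six week-4 endpoints, against a nominal 5%. These sizes depend on 40 per arm, equal arms and correlation 0 to 0.9, and the second also on the assumed response rates. The direction does not depend on the exact values: two 5% tests, either of which suffices, exceed 5% unless they always reject together. The remaining uncertainty is which decision rule was intended, and that is the gap to be closed.

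**What to change.** Name one primary endpoint, for example the reduction from baseline in attack frequency over the 4 weeks, and say what the baseline is. Test the three arms together at two-sided 0.05 (ANOVA or Kruskal-Wallis), and test the three pairs at 0.05 only if that test is significant. With three arms this holds the error at about 5%: once one arm differs, at most one pair is still truly equal. Simulated values are 4.6–5.2%. For Kruskal-Wallis followed by Mann-Whitney on count data they are 4.9% with all arms equal and 5.2% with one arm different.

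Label VAS, the response rates and any weekly comparisons as secondary, with 95% confidence intervals and no confirmatory claim. Label the within-arm tests as descriptive and not evidence of a difference between treatments.

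If both outcomes must stay primary, use 0.025 for the three-group test and for the gated pairs of each outcome (simulated 3.4–5.2%). Leaving the pairs at 0.05 is not enough: with one arm different on both outcomes, one truly equal pair remains for each, and 1 − 0.95² = 9.75% (simulated 6–10%).

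If results were already known when the primary is chosen, label all results exploratory, that endpoint included. A primary picked as the more significant of the two outcomes carries the 7–10% error, and one picked from all six carries 17–22%.

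The cost is a few sentences in the Statistical analysis section, and fewer results can be called significant. With two primaries at 0.025, the pairwise difference detectable with 80% power (40 v 40) rises from about 0.63 to 0.70 SD for the pair test alone. When the three-group gate must also be passed and one arm differs, it rises from about 0.67 to 0.73 SD.
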